6.4 Treatment Period: (Day 1 to Day 21)

6.4.1 Day 1 of each cycle

- Serum chemistry panel (within 1 day before dosing)
- CBC with differential (within 1 day before dosing)
- SGN-35 administration (see Section 5.2)
- Vital signs
- Weight
- Physical examination (see Section 7.3)
- Karnofsky performance status (Appendix Section 14.2)
- B symptom assessment

6.4.2 Disease Response Assessments

Responses will be assessed (between Days 15 and 21) as follows as defined in Section 7.1:

- Dedicated CT of chest, neck, abdomen, and pelvis or CT/PET: Cycles 2 and 4
- PET: Cycle 4

In addition, bone marrow aspirate and biopsy are required to confirm responses in patients who have bone marrow involvement at baseline (see Section 7.1). The follow-up bone marrow aspirate and biopsy must be done within 2 weeks of documentation of response. Once the bone marrow is negative no further bone marrow evaluations are required.

6.5 End of Treatment (21 ± 7 days after last dose of SGN-35)

Note: End of Treatment (EOT) evaluations should be obtained before initiation of non-protocol therapy.

- Electrocardiogram
- Serum chemistry panel
- CBC with differential
- Pregnancy test
- Weight
- Physical exam
- Karnofsky performance status (Appendix Section 14.2)
- Response assessment (if a radiologic assessment has not been performed within the prior 6 weeks)
- B symptom assessment

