6.2 Screening/Baseline: Days -28 to -1

- Informed consent
- Study eligibility per inclusion/exclusion criteria (see Section 4.1 and 4.2)
- Medical history
- Prior disease therapies
- Dedicated CT of chest, neck, abdomen and pelvis and CT/PET (allow up to 5 day window. Days -33 to -1)
- Bone marrow aspirate and biopsy (Note: may not need to be performed if patient had a bone marrow biopsy done at diagnosis and there was no bone marrow involvement. If a prior history of bone marrow involvement at diagnosis, a repeat

bone marrow biopsy must be done to document bone marrow status 30 days prior to 1st dose of SGN-35. If the patient had undergone another bone marrow biopsy at the time of relapse with positive involvement, and no other intervening therapy was given prior to SGN-35, no additional bone marrow biopsy is needed in the screening /baseline period).

- B symptom assessment

6.3 Screening/Baseline: Days -7 to Day 1

- Physical examination (see Section 7.3)
- Height
- Electrocardiogram
- Serum chemistry panel (see Section 7.2)
- Complete blood count (CBC) with differential (see Section 7.2)
- Pregnancy test
- Karnofsky performance status (Appendix Section 14.2)

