7.1 Response Assessments

Treatment response will be assessed by dedicated spiral CT scan of chest, neck, abdomen, and pelvis and PET scans performed at protocol-specified time points (see Appendix Section 14.1 and Section 6). The determination of antitumor efficacy will be based on objective response assessments made according to the Revised Response Criteria for Malignant Lymphoma (Cheson et al. 2007) and treatment decisions by the investigator will be based on these assessments. Clinical response of progressive disease (PD), stable disease (SD), partial remission (PR), or complete remission (CR) will be determined at each assessment. Selection of up to 6 of the largest dominant nodes or nodal masses to follow for response assessment must be PET FDG-avid at baseline. Investigator evaluation of baseline radiographic assessment will enable study enrollment per Inclusion Criteria based on the presence of measurable disease > 1.5 cm evidenced by CT scan of the neck/chest/abd/pelvis or CT/PET scans. In addition, per the Revised Response Criteria for Malignant Lymphoma, these nodes or masses should be selected according to all of the following: they should be clearly measurable in at least 2 perpendicular dimensions; if possible they should be from disparate regions of the body; and they should include mediastinal and retroperitoneal areas of disease whenever these sites are involved.

If the bone marrow was positive at baseline, a follow-up bone marrow aspirate and biopsy is required and must be negative for assessment of a CR. If the follow-up

morphology is indeterminate, the biopsy tissue must be negative by immunohistochemistry or the patient will be assessed as a PR.

Tumor imaging will be performed at screening, cycle 2, and 4.

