In accordance with the primary study objectives, we will perform descriptive statistical analyses on these data after the study is complete. With adequate follow-up time, the endpoints of PFS, overall survival (OS) will be assessed by Kaplan-Meier survival analysis and 95% confidence intervals will be calculated using Greenwood's formula. PFS will be defined as the time from first treatment day (post AHCT) until objective or symptomatic relapse or death as a result of lymphoma or acute toxicity of treatment. OS will be defined as the time from first treatment day (post AHCT) until death. The cumulative incidence of relapse/progression and non-relapse mortality will be calculated as competing risks.

8.2 New Cohort to Test Increased Dosing for Patients Not Achieving CR after Two Cycles

Based on previously published brentuximab vedotin response/toxicity data and data from the phase II portion of this study (see protocol section 1.3), we now propose to accrue up to 20 additional patients in a new cohort that will enroll until we have 10 patients who do not attain CR after two cycles of therapy, and are treated at the increased dose of 2.4 mg/kg of brentuximab vedotin for cycles 3 and 4. The goal of this study is to evaluate the impact of treating non-CR patients (after two cycles of therapy) at an increased dose (from 1.8 mg/kg to 2.4 mg/kg) during cycles 3 and 4. We believe that the 2.4 mg/kg dose will be well tolerated (defined as $\leq 33\%$ of patients with \geq grade 3 non-hematologic toxicity that is assigned an attribution level of at least possibly related to the study drug during cycle 3 or 4) and that treating these patients at the increased dose will increase the CR rate.

With a CR rate of 33.3% -after two cycles of therapy, we expect to achieve 10 patients without CR (in the first 2 cycles) after 15 patients are enrolled (maximum enrollment 20, which has $>90\%$ chance of having 10 patients without CR in first two cycles). With 10 patients treated at the escalated dose of 2.4 mg/kg, with a conversion rate of 25%, the probability of not getting at least one response is less than 6%. If the first 2 cycle response data are pending, accrual will not hold. Accrual will only hold based on stopping due to toxicity, or when 10 patients are treated at the escalated dose of 2.4mg/kg. Patients who are treated with at least one cycle at 2.4 mg/kg will be evaluable at that dose level, even if later dose reduced or discontinued.

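### The six-week waiver on the End of Treatment scan lets the cycle 2 scan stand in for one at 2.4 mg/kg, so a new-cohort patient who stops after one higher dose need not be imaged on it

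*Combined protocol and SAP*

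**What the plan says.** **Imaging schedule.** Section 6.4.2 sets the timing: "Responses will be assessed (between Days 15 and 21) as follows". It names the cycles: "Dedicated CT of chest, neck, abdomen, and pelvis or CT/PET: Cycles 2 and 4". Section 7.1 agrees: "Tumor imaging will be performed at screening, cycle 2, and 4". No scan is scheduled in cycles 1 or 3. Section 6.2 lets baseline imaging fall some weeks before treatment: "allow up to 5 day window. Days -33 to -1".

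**EOT visit.** Section 6.5 is titled "End of Treatment (21 ± 7 days after last dose of SGN-35"), so the visit falls 14 to 28 days after the last dose. The imaging item there is conditional: "Response assessment (if a radiologic assessment has not been performed within the prior 6 weeks"). A note asks that EOT evaluations precede non-protocol therapy.

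**New cohort.** Under section 4.3, imaging after two cycles at 1.8 mg/kg must show partial remission (PR) or stable disease (SD) before a patient can receive 2.4 mg/kg. That scan therefore precedes the first higher dose. Section 8.2 says that a patient with at least one cycle at 2.4 mg/kg "will be evaluable at that dose level, even if later dose reduced or discontinued". Accrual ends once 10 patients have been treated at that dose. Section 2.3 makes response and toxicity after cycle 4 at the higher dose an objective of the cohort. Section 8.1 calculates response rates over evaluable patients.

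**The concern.** A patient who stops after cycle 3 never reaches the cycle 4 scan, so the EOT assessment is the only one the protocol offers after a 2.4 mg/kg dose. The waiver can remove it on the strength of a scan taken before that dose was given. The only required response result is then the PR or SD seen at 1.8 mg/kg. Stopping at this point is foreseen: the dose-modification section for 2.4 mg/kg patients includes discontinuation for toxicity.

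The cohort exists to learn whether the higher dose converts non-CR patients. It has 10 such patients, each worth 10 percentage points, and an unscanned patient still fills one of the 10 places. The gap may also be permanent. Section 1.4 reports that most main-cohort patients in PR or SD went on to combination chemotherapy, and a scan taken after that could not be credited to brentuximab vedotin.

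**Working it through.** **The plan's own figure.** Section 8.2 gives 10 patients, a 25% conversion rate and a probability below 6% of no response. (1 - 0.25)^10 = 0.75^10 = 0.0563, or 5.6%. This reproduces, provided each of the 10 can be observed to convert.

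**Age of the cycle 2 scan at EOT after one 2.4 mg/kg dose.** Inputs:
- Cycle 2 scan on Days 15-21 (6.4.2), with an on-time cycle 3 Day 1 on cycle 2 Day 22 (21-day cycle, 5.2). The scan is then g = 1 to 7 days before the dose.
- Cycle 3 start delayed by d days, with d = 0 to 21 (second section 5.5).
- EOT at e = 14 to 28 days after the dose (6.5).
- Waiver limit: 6 weeks = 42 days (6.5).

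Scan age = g + d + e.

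| Delay d (days) | Age over the whole EOT window | Age at a day-21 visit | Scan required? |
|---|---|---|---|
| 0 | 15-35 | 22-28 | No |
| 7 | 22-42 | 29-35 | No |
| 8 | 23-43 | 30-36 | Only at the extreme |
| 14 | 29-49 | 36-42 | Late in the window only |
| 21 | 36-56 | 43-49 | Yes at day 21; not always earlier |

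With d of 7 or less and e of 28 or less, the age cannot exceed 7 + 7 + 28 = 42. Two things can make the waiver lapse: cycle 3 starts more than 7 days late, or the EOT visit slips past day 28. The second can follow a long hold before an abandoned cycle 4. With an on-time cycle 3, a hold of h days and EOT at 21 + h days, the scan is 22 + h to 28 + h days old. That can exceed 42 only when h > 14, and is 43-49 days at h = 21.

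**Stopping after cycle 1.** Take a baseline scan k days before the first dose and EOT on target at 21 days. Its age is k + 21, which is at most 42 when k is at most 21. Read literally, a baseline scan on Day -21 or later also waives this assessment.

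**Effect on the cohort's figures.** The documents give no rate of stopping after one 2.4 mg/kg dose, so 1 to 3 unscanned patients is an assumption.

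| Unscanned of 10 | Chance of no observed conversion at 25% |
|---|---|
| 0 | 0.75^10 = 5.6% |
| 1 | 0.75^9 = 7.5% |
| 2 | 0.75^8 = 10.0% |
| 3 | 0.75^7 = 13.3% |

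The denominator matters too. Two conversions with two unscanned patients is 2/10 = 20% if they are counted and 2/8 = 25% if they are left out.

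**The case against.** Several stronger readings are tempting, and the documents do not support them.

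- *Such patients are never scanned, or the waiver always applies.* Section 6.5 says when a scan is not required; it forbids none. The working also shows that a late cycle 3 or a late EOT visit can restore the requirement. What stands is that the protocol does not require the scan when cycle 3 is on time and EOT is in its window.
- *Section 8.2 insists on keeping these patients in the conversion rate.* It does not say whether evaluable means for toxicity, response or both. The sentence closely follows one on stopping for toxicity, and for toxicity the rule is sound. If it means toxicity only, the response denominator at 2.4 mg/kg is simply not stated.
- *The scoring of unscanned patients biases the CR rate.* Patients reach 2.4 mg/kg only with PR or SD, so carrying the cycle 2 result forward and counting a non-converter give the same CR count. The loss lies in conversions that go unseen and in whether the patient stays in the denominator.
- *The primary response rate of the main cohort is at risk.* Sections 1.4 and 5.5 describe 37 patients as already treated, which is the full planned sample in sections 4 and 8.1. A change to 6.5 cannot recover their scans. The cycle 1 case matters only for new-cohort patients, and treating an eligibility scan as grounds to skip a response assessment is literal but strained.

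On size, the objection is fair. The 5.6% figure credits an early stopper with the full 25% chance of conversion, which is doubtful for someone who stops for clinical worsening. For one such patient, scanning improves the figure by at most 7.5 - 5.6 = 1.9 percentage points, and by nothing if one dose could not have converted that patient. Section 8.2 also attaches no decision rule to the figure.

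**Conclusion.** The point holds as a limited defect in a stated rule. With an on-time cycle 3 and an in-window EOT visit, the scan that preceded 2.4 mg/kg is 15-35 days old and excuses the only assessment a patient stopping after one higher dose would have. CR conversions at that dose could then be missed, and section 8.2 leaves open how such a patient enters the response analysis. The probability of seeing no conversion would rise from 5.6% to 7.5%, 10.0% or 13.3% under an assumed 1, 2 or 3 unscanned patients; one is enough to pass the stated 6%.

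This rests on sections 6.4.2, 6.5 and 7.1 giving the whole imaging schedule. The study flow chart (Appendix 14.1) was not in the text available and could not be checked. The consequence is confined to a small, descriptive cohort, but the data concern that cohort's own question and may not be obtainable later.

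**What to change.** In section 6.5, replace the imaging item with: *Response assessment (unless a radiologic assessment was performed on or after Day 15 of the last cycle received), before initiation of non-protocol therapy.* This is a single trigger that matches the existing Day 15-21 scan window. Patients with an in-window scan in cycle 2 or 4 who stop after that cycle remain excused.

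In section 8.2, add that the report will give the number of 2.4 mg/kg patients who had a scan after a 2.4 mg/kg dose, and that those without one count as non-converters and are listed separately. State there whether evaluable covers toxicity, response or both.

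The cost is one line and a sentence or two. The EOT assessment already exists and only its trigger changes. The downside is one scan in the few patients who stop after cycle 1 or 3 and are now excused. It takes the place of the cycle 4 scan that they will not have, and no dose or treatment rule changes.

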7 STUDY ASSESSMENTS

Only patients who meet all inclusion and exclusion criteria specified in Section 4 will be enrolled onto this study.

7.1 Response Assessments

Treatment response will be assessed by dedicated spiral CT scan of chest, neck, abdomen, and pelvis and PET scans performed at protocol-specified time points (see Appendix Section 14.1 and Section 6). The determination of antitumor efficacy will be based on objective response assessments made according to the Revised Response Criteria for Malignant Lymphoma (Cheson et al. 2007) and treatment decisions by the investigator will be based on these assessments. Clinical response of progressive disease (PD), stable disease (SD), partial remission (PR), or complete remission (CR) will be determined at each assessment. Selection of up to 6 of the largest dominant nodes or nodal masses to follow for response assessment must be PET FDG-avid at baseline. Investigator evaluation of baseline radiographic assessment will enable study enrollment per Inclusion Criteria based on the presence of measurable disease > 1.5 cm evidenced by CT scan of the neck/chest/abd/pelvis or CT/PET scans. In addition, per the Revised Response Criteria for Malignant Lymphoma, these nodes or masses should be selected according to all of the following: they should be clearly measurable in at least 2 perpendicular dimensions; if possible they should be from disparate regions of the body; and they should include mediastinal and retroperitoneal areas of disease whenever these sites are involved.

If the bone marrow was positive at baseline, a follow-up bone marrow aspirate and biopsy is required and must be negative for assessment of a CR. If the follow-up

morphology is indeterminate, the biopsy tissue must be negative by immunohistochemistry or the patient will be assessed as a PR.

Tumor imaging will be performed at screening, cycle 2, and 4.

7.2 Clinical Laboratory Evaluations

Samples will be drawn for local labs. All clinical decisions will be based on local lab results. The following laboratory assessments will be performed to evaluate safety at scheduled timepoints (see Appendix Section 14.1) during the course of the study:

- Chemistry panel, including sodium, chloride, potassium, blood urea nitrogen (BUN), lactate dehydrogenase (LDH), creatinine, calcium, albumin, glucose (fasting levels are to be assessed at baseline; non-fasting levels are to be assessed at other timepoints), total bilirubin, alkaline phosphatase, ALT, AST, ESR, and uric acid.
- The hematology panel includes the following tests: white blood cell count, hemoglobin/hematocrit, platelets and the differential includes: neutrophils, lymphocytes, monocytes, eosinophils, and basophils.

7.3 Other Study Assessments

Other study assessments include the following:

- Biopsies for CD30 expression: Results of CD30 expression from the most recent post-diagnostic biopsy of relapsed/refractory disease may be obtained from pathology reports of an archived tumor block or slides or a fresh biopsy to enable study enrollment (per inclusion criteria). The archived tumor block or slides must be submitted for central pathology review. In addition, a tumor block or slides from the original diagnostic biopsy should be submitted when available. These should be submitted to the pathology department
- Patient medical history, including a thorough review of:
 - The patient's current and previous conditions.
 - Disease status after each previous systemic therapy received prior to entering this study.
 - Concomitant medications and prior therapies.
- Physical examination, including evaluation of skin, HEENT (head, eyes, ears, nose, and throat), nodes, heart, lungs, abdomen, back, extremities, and neurology.
- Karnofsky performance status (see Appendix section 14.2).
- B symptom assessment (unexplained fevers greater than 38°C, drenching night sweats and/or weight loss greater than 10% of body weight).
- Electrocardiogram.
 - FACT/GOG Neurotoxicity questionnaire to be done at screening, before every cycle and at the end of study visit.

- Tumor biopsies for patients who develop progressive disease during the course of brentuximab vedotin therapy as long as medically safe (optional)

7.4 Pharmacodynamic/Pharmacogenomic/Correlative Studies

A paraffin block from the representative diagnostic section or 12 unstained paraffin slides will be obtained from diagnostic materials and also at the time of relapse (if available). We will analyze for CD 30 and CD 68 expression. We will confirm CD 30 expression prior to enrollment in trial. Patients must have CD 30 expression in original diagnostic material or relapsed material. We will examine the CD 68 expression in the original and relapsed material and attempt to correlate with response. For patients who have biopsy material available at relapse or progression, we will collect DNA/RNA from the tumor specimen and perform microarray analysis and compare with before and after treatment.

7.5 Safety Measurements

Safety measurements will consist of monitoring and recording all adverse events, including serious adverse events, the regular monitoring of hematology, serum chemistry, routine monitoring of vital signs (heart rate, blood pressure, and body temperature) and physical condition. Toxicity will be assessed using the NIH-NCI Common Terminology Criteria for Adverse Events, Version 4.0.

8 STATISTICAL PROCEDURES.

8.1 Sample size calculations.

The aim of this study is to estimate the efficacy of this salvage brentuximab vedotin treatment for Hodgkin lymphoma prior to autologous hematopoietic stem cell transplantation. Treatment will be given once every three weeks in a 21 day cycle. Based on historical data, the assumed ORR in this patient population is 60%. The objective of this study is to be able to detect an ORR of at least 60%. The study will utilize a Simon two-stage optimal design. Twenty three (23) subjects will be enrolled in the first stage. If 12 or more subjects respond, an additional 14 subjects will be enrolled (for a total sample size of 37). The null hypothesis will be rejected if 23 or more of the total sample size of 37 respond. This design is based on the use of a two sided test at the 5% level of significance and provides 80% power.

Analysis: Response rates will be calculated as the percent of evaluable patients that have confirmed CR or PR by radiographic response including CT and/or PET scans, and exact 95% confidence intervals will be calculated for this estimate. Time to response, duration of response, and survival will be estimated using the product-limit method of Kaplan and Meier. Toxicity information recorded will include the type, severity, and the probable association with the study regimen. Tables will be constructed to summarize the observed incidence by severity and type of toxicity. Baseline information (e.g. the extent of prior therapy) and demographic information will be presented, as well, to describe the patients treated in this study.

Based on the current referral patterns it is expected that 37 patients will be enrolled in this study over the course of 3 years.

In accordance with the primary study objectives, we will perform descriptive statistical analyses on these data after the study is complete. With adequate follow-up time, the endpoints of PFS, overall survival (OS) will be assessed by Kaplan-Meier survival analysis and 95% confidence intervals will be calculated using Greenwood's formula. PFS will be defined as the time from first treatment day (post AHCT) until objective or symptomatic relapse or death as a result of lymphoma or acute toxicity of treatment. OS will be defined as the time from first treatment day (post AHCT) until death. The cumulative incidence of relapse/progression and non-relapse mortality will be calculated as competing risks.

8.2 New Cohort to Test Increased Dosing for Patients Not Achieving CR after Two Cycles

Based on previously published brentuximab vedotin response/toxicity data and data from the phase II portion of this study (see protocol section 1.3), we now propose to accrue up to 20 additional patients in a new cohort that will enroll until we have 10 patients who do not attain CR after two cycles of therapy, and are treated at the increased dose of 2.4 mg/kg of brentuximab vedotin for cycles 3 and 4. The goal of this study is to evaluate the impact of treating non-CR patients (after two cycles of therapy) at an increased dose (from 1.8 mg/kg to 2.4 mg/kg) during cycles 3 and 4. We believe that the 2.4 mg/kg dose will be well tolerated (defined as $\leq 33\%$ of patients with \geq grade 3 non-hematologic toxicity that is assigned an attribution level of at least possibly related to the study drug during cycle 3 or 4) and that treating these patients at the increased dose will increase the CR rate.

With a CR rate of 33.3% -after two cycles of therapy, we expect to achieve 10 patients without CR (in the first 2 cycles) after 15 patients are enrolled (maximum enrollment 20, which has $>90\%$ chance of having 10 patients without CR in first two cycles). With 10 patients treated at the escalated dose of 2.4 mg/kg, with a conversion rate of 25%, the probability of not getting at least one response is less than 6%. If the first 2 cycle response data are pending, accrual will not hold. Accrual will only hold based on stopping due to toxicity, or when 10 patients are treated at the escalated dose of 2.4mg/kg. Patients who are treated with at least one cycle at 2.4 mg/kg will be evaluable at that dose level, even if later dose reduced or discontinued.

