11.1.2 Monitoring and Personnel Responsible for Monitoring

The Protocol Management Team (PMT) consisting of the PI, Collaborating Investigator, CRA/protocol nurse, and statistician is

responsible for monitoring the data and safety of this study, including implementation of the stopping rules for safety and efficacy.

Data and safety will be reported to the COH DSMC using the PMT report and submitted quarterly from the anniversary date of activation. Protocol specific data collection will include the following items: hematological response, and toxicities of treatment. Reporting of data and safety to the DSMB will occur at the time of planned endpoints or unanticipated problems and at least once per year using the PMT report. The planned endpoint is overall response rate as determined by radiographic imaging after 2nd and 4th cycle of treatment. We will perform interim analysis after 17 patients have accrued on study and report to the DSMB and also after 37 patients have accrued on study.

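### The response cut-offs in section 8.1 do not match the design, error level and power stated beside them; if the null was 50%, the final cut-off is one responder too low and one-sided error is 9.3%

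*Combined protocol and SAP*

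**What the plan says.** Section 8.1 (Sample size calculations) names the design: "The study will utilize a Simon two-stage optimal design". The first stage is set by "Twenty three (23) subjects will be enrolled in the first stage", the continuation rule by "If 12 or more subjects respond, an additional 14 subjects will be enrolled (for a total sample size of 37"), and the final rule by "The null hypothesis will be rejected if 23 or more of the total sample size of 37 respond". The claimed properties follow: "This design is based on the use of a two sided test at the 5% level of significance and provides 80% power".

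One response rate is given, in two roles. It is the historical or assumed rate ("Based on historical data, the assumed ORR in this patient population is 60" per cent) and also the rate to be detected ("The objective of this study is to be able to detect an ORR of at least 60" per cent). No separate null and target rates appear. The same section promises exact 95% confidence intervals for the response rate.

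Section 1.4 reports that 37 patients have been treated in the phase II portion, with an ORR of 75% in 30 evaluable patients.

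**The concern.** A Simon design is defined by a null rate, a target rate, an error level and a power. The cut-offs follow from those four. Section 8.1 gives the cut-offs, the error level and the power but no usable pair of rates, so the stated 5% and 80% have to be checked against the rule as written.

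Two features suggest a transcription slip. First, published Simon designs list r1/n1 and r/n, where r1 and r are the largest counts that still fail. A rule copied from such a table but worded as that number or more is one responder too lenient at each stage. Second, a rule with a single upper rejection bound is one-sided, whatever the label says.

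At stake is the error rate attached to the primary efficacy test. If the null was 50%, the plan could also declare success while the 95% interval reported beside the result contains the null.

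**Working it through.** **Inputs.** From section 8.1: n1 = 23, n2 = 14, N = 37; continue at a1 = 12 or more; reject at a = 23 or more; stated error 5% two-sided, power 80%; rate 60%. Assumed, not in the documents: null 50% and target 70%, inferred in step 2.

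**Formula.** With Bin the binomial distribution,

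P(reject | p) = Σ over x ≥ a1 of P[Bin(23, p) = x] × P[Bin(14, p) ≥ a − x].

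**Step 1: the plan's own figures.** At p = 60% the written rule rejects with probability 0.461. If 60% is the null, error is 46%. If 60% is the target, power is 46%. Neither stated figure is reproduced. The standard one-sided 5%/80% designs that use 60% in either role also have other sizes, written as r1/n1, r/N:

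- 40% versus 60%: optimal 7/16, 23/46; minimax 17/34, 20/39.
- 60% versus 80%: optimal 7/11, 30/43; minimax 8/13, 25/35.

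**Step 2: where 23 and 37 could come from.** Optimal and minimax designs were searched at one-sided 2.5%, 5% and 10% with 80% power, and at 5% and 10% with 90% power. The grid was in 5-point steps (null from 10%, target up to 95%, gaps of 15 to 25 points). For 5%/80% a 1-point grid was added (null 40% to 61%, gaps of 17 to 23 points). Stages of 23 and 37 came up once:

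- 50% versus 70%, one-sided 5%, 80% power, **minimax**: 12/23, 23/37, that is, continue at 13 or more and reject at 24 or more (expected size under the null 27.7).
- The **optimal** design for the same pair is 8/15, 26/43 (expected size 23.5).

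All four numbers of the minimax design (12, 23, 23, 37) are printed in section 8.1, but 12 and 23 responders appear there as passing counts.

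**Step 3: the written rule at 50% versus 70%, and which cut-off matters.**

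| Rule | One-sided error at 50% | Power at 70% |
|---|---|---|
| ≥12/23, ≥23/37 (as written) | 9.27% | 88.45% |
| ≥13/23, ≥23/37 (stage 1 changed only) | 8.81% | 87.27% |
| ≥12/23, ≥24/37 (final changed only) | 4.93% | 80.64% |
| ≥13/23, ≥24/37 (minimax design) | 4.82% | 80.11% |

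The stage 1 cut-off contributes 9.27 − 8.81 = 0.46 percentage points. As a check, that is the x = 12 term of the sum at p = 50%: 0.1612 × 0.0287 = 0.0046. The final cut-off contributes 9.27 − 4.93 = 4.34 points.

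**Step 4: the written rule over a range of nulls.**

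| Null rate | 40% | 45% | 47% | about 47.4% | 50% | 55% | 60% |
|---|---|---|---|---|---|---|---|
| One-sided error | 0.5% | 2.6% | 4.6% | 5.0% | 9.3% | 23.7% | 46.1% |

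An upper tail of 2.5%, which is what a two-sided 5% test allows, holds only for a null up to about 44.8%. Power reaches 80% from a target of about 67.35%.

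**Step 5: exact (Clopper-Pearson) intervals.** 95%: 23/37, 44.8% to 77.5%; 24/37, 47.5% to 79.8%; 25/37, 50.2% to 82.0%. 90%: 24/37, 50.05% to 77.8%. At a 50% null, a result of 23 or 24 responders sits beside a 95% interval that contains the null. The 90% interval, which corresponds to a one-sided 5% test, excludes 50% at 24.

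**The case against.** The main objection is that 50% and 70% are nowhere in the documents. A reader might infer that the trial runs at 9% error outright. The documents do not support that: the figure is conditional on an inferred null, and step 4 shows how far it moves. The match on all four numbers makes 50% versus 70% a likely origin but does not prove it. Section 11.1.2 adds some doubt, since it places the interim look elsewhere ("We will perform interim analysis after 17 patients have accrued on study") and not at the 23-patient first stage.

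A reader might also infer that stating the null and target could not rescue the rule. It could. At 47% versus 68%, for example, the written rule has 4.6% error and 82.3% power. With a null of 44.8% or lower and a target above about 67.35% it even meets a 2.5% upper tail with 80% power. What tells against this reading is that such pairs are unusual, section 8.1 states none of them, and minimax searches at several (47% versus 68% and 46% versus 67% among them) did not return 23 and 37.

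A third tempting reading is that both cut-offs cause the inflation. Step 3 shows otherwise: the stage 1 cut-off is a mismatch with the minimax design and adds under half a percentage point.

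Timing also counts. Section 1.4 indicates that stage 1 is over and that interim results are known, so raising the final bar now is a change made after data were seen and not a neutral edit. This objection stands and shapes the fix.

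Finally, the correction treats 5% as one-sided, whereas section 8.1 says two-sided. Keeping two-sided 5% at 50% versus 70% with 80% power would need 48 patients (minimax) or 57 (optimal). With 37 patients a cut-off of 25 gives 2.3% to 2.4% error but only about 70% power.

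**Conclusion.** Section 8.1 is wrong as written. The rule does not give the stated 5% and 80% at the only rate supplied (46% rejection at 60%). It also departs from the one standard design found with its stage sizes: that design is minimax rather than optimal and one-sided rather than two-sided, and it passes at 13 and 24 rather than 12 and 23.

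If the null was 50% and the target 70%, one-sided error is 9.3% against a stated 5%, and power is 88.5% against a stated 80%. This size rests on the inferred pair and on one-sided testing; the error ranges from 2.6% at a null of 45% to 46% at 60%.

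A reader might conclude that the trial's finding is in doubt. Nothing in the documents points that way. If the final ORR is near the interim 75% (0.75 × 37 = 27.75, about 28 of 37), the result passes at 23 or at 24. The defect lies in the error and power attached to the primary test.

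**What to change.** In section 8.1:

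- State the null and target response rates, and reconcile them with the two uses of 60%.
- Call the test one-sided and give its level.
- If 50% versus 70% was intended, name the design minimax and leave the stage 1 decision as it was made. Then do one of two things: (a) set the final cut-off to 24 or more of 37, with exact error 4.9% and power 80.6%, disclosed and dated as a change made after interim data were known; or (b) keep 23 or more and restate error as 9.3% and power as 88.5%.
- If another pair was intended, report the exact error and power of the written rule at that pair.
- Report a 90% exact interval beside the 95% one, so that interval and one-sided test agree at the cut-off of 24 (90% lower limit 50.05%).

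The cost is a revision of section 8.1 and no extra patients. Option (a) raises the bar by one responder and lowers power at 70% from 88.5% to 80.6%. Option (b) changes no decision rule but acknowledges a higher error rate.
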